#### IV. STUDY DESIGN

#### V. STUDY ENROLLMENT

##### a) Recruitment and Screening for Eligibility

Women will be recruited for the study by study nurses from the waiting room for the antenatal care clinic at one of 2 CBCHS facilities; Mboppi Hospital in Douala and the Baptist Hospital in Mutengene. Study eligibility will be assessed using a standardized form by study nurses with review of the medical record and discussion with the patient in a private room. Subjects will be consented prior to any study procedures.

If the patient appears to meet the criteria for enrollment and expresses interest in the study, she will be told more details about the study and asked to sign the informed consent. The consent form will be available in English and in French. For patients who only understand Pidgin English or are not literate, the study will be explained verbally by the study nurse and the consent will be read aloud. A support person or family member will be allowed to help with the consent process if the patient prefers this option.

##### b) Participant Inclusion Criteria

- Confirmed HIV-infection (documented in medical record)
- Age  $\geq 16$  years
- Confirmed pregnancy,  $<28$  weeks estimated gestational age (by best obstetric estimate which may include ultrasound or fundal height and LMP)
- Live singleton pregnancy

- Receiving prenatal care at Mboppi Hospital or Mutengene Hospital
- Plan to receive follow up prenatal care and deliver at study facility
- Capable of providing written informed consent
- Able and agree to come to facility for febrile episodes or acute illness during pregnancy (with reimbursement of transportation costs).
- Agree to avoid antimalarial medications outside of study protocol.
- Women receiving standard therapy for HIV infection (any antiretroviral regimen) and standard malaria prophylaxis medications (cotrimoxazole) will be eligible to participate.
- Women with HIV-infection who are not taking antiretrovirals (for any reason) are eligible to participate in the trial if all other study criteria are met.
- Participants will be eligible to participate irrespective of prior or active malaria infection detected at the time of study enrollment.

### **c) Participant Exclusion Criteria**

- Severe anemia (last hemoglobin <6)
- History of severe adverse reaction to co-trimoxazole or azithromycin
- Active medical problem requiring inpatient evaluation at the time of screening
- Intention of moving far away from the facility during pregnancy or not likely to return for follow up care or delivery
- Signs or symptoms of early or active labor
- Known congenital anomalies
- History of severe cardiac disease (including congestive heart failure, severe valvular disease or arrhythmias).

### **d) Randomization Method and Masking**

Consenting women will be assigned to one of two prophylaxis groups with a computer generated variable size (2, 4, 6) block randomization sequence prepared in advance by a co-investigator at the University of Alabama at Birmingham. The active and placebo study medication will be indistinguishable in appearance and packaged according to the randomization sequence so that the patient is randomized when she is assigned to the next available individual supply of study medication. The study is double masked; neither the patient nor the clinical staff will be aware of the assigned prophylaxis.

Randomization will be stratified by clinical center to assure balance between the two study groups with respect to anticipated differences among the clinic populations and possible differences in patient management. A unique study ID will be provided to each patient after they are randomized (starting with 5001D for the Douala site, starting at 9001M for the Mutengene site).

The PI and all staff responsible for assessing outcomes (laboratory and clinical) will be blinded to the randomization arm.

## VI. STUDY INTERVENTION

### a) Study Product Description and Storage

The medications are to be taken orally as pills. They are stable at room temperature in Cameroon. The supply will be maintained by the study nurse on site. The TMPS will be acquired in Cameroon per routine procurement pathways at CBCHS. The CBCHS Pharmacy has internal policies and procedures to verify the quality of the antibiotics administered on site. The azithromycin and matching azithromycin placebo will be created by a US Pharmaceutical Company (Goderich Pharmacy, Houston, TX) and shipped to the Central Pharmacy in Mutengene, Cameroon where the study drugs will be packaged for dissemination.

### b) Administration of Study Product

Study nurses will have 30 day supply of medications prepared in advance for each subject according to their study ID. TMPS (1 DS tab 160/800 mg po QD) is routinely offered in clinic and this will be provided for women in both groups. Women will also receive a 1 gram dose (two 500 mg pills) of azithromycin (AZ) or AZ placebo under directly observed therapy and this will be recorded. Subjects will be observed for 5 minutes for adverse events. Women will be sent home with 4 additional azithromycin or placebo pills with written instructions on the bag to take 2 pills on the morning of day #2 and 2 pills on the morning of day #3 after the study visit. The azithromycin has a 2-year shelf life at room temperature.

### c) Assessment of Participant Compliance with Study Intervention

Study subjects will be reminded that they will be asked about adherence, tolerance and side effects at the subsequent visit. They will complete a medication adherence questionnaire (MAQ) at subsequent visits.

### d) Concomitant Medications/Treatments

Subjects will be encouraged to continue daily antiretroviral therapy throughout pregnancy. They will be advised not to take any outside medications to treat or prevent malaria without discussing it with the study nurse. Antipyretics and any other medications without antimicrobial properties are allowed. All medications taken will be captured at each follow up visit.

## VII. STUDY SCHEDULES AND PROCEDURES

	Screen and Enroll	Follow up Visit (1-6)	Sick Visit (1-9)	Term Visit (1)	Delivery Visit (1)	Postpartum (if no Delivery Visit)	Follow Up Call	Infant Follow Up Call or Visit
Timing of Visit/Call	4-28 weeks	Every 4 weeks	As Needed	35-42 weeks	At Delivery	Within 14 days of delivery 	Within 6 weeks	3, 6, 9, 12 months
FORMS 								
Screening Log (Form 1)	X							
Eligibility (Form 2)	X							
Consent and Randomize (Form 3,4)	X							
Baseline Survey (Form 5)	X							
Follow Up Survey (Form 6)		X		X	X	X		
Med Adherence (Form 7)		X	X	X	X	X		
Sick Call Survey (Form 8)			X					
Outcomes and Labs (Form 9)	X	X	X	X	X	X	X	
Adverse Events (Form 10)		X	X	X	X	X	X	X
Postpartum Phone Call (F 11)							X	
Participant Contact Info (Form 12)	X	X	X	X	X	X	X	
Infant Follow Up (Form 13)								X
CLINICAL AND SAMPLING								
Vitals and Exam	X	X	X	X	X	X		
Venipuncture	X		X	X	X	X		
Finger stick	X	X	X	X	X	X		
Vaginal Swab	X			X	X	X		
Placental biopsy					X			
Directly Observed Therapy	X	X	X	X				
LAB TESTING 								
CBC and differential	X			X	X	X		
CD4 Count				X				
HIV Viral Load					X			
Thick smear	X			X	X	X		
RDT		X	X	X				
DBS for PCR	X	X	X	X	X	X		
Syphilis (RPR/TPHA)	X 			X	X	X		
Xpert GC/CT & GBS NAAT				X	X	X		
SUPPLIES PROVIDED								

Bed Net	X							
Condoms	X	X	X	X				
30 day med supply	X	X	X	X				

 Samples collected at postpartum visit only if they were not collected at prior visits

 Lab testing to be performed on site. Additional testing at UAB is not part of this table.

 In cases of fever or clinical suspicion of malaria.

 RPR testing will be performed for women with a positive treponemal test on enrollment if it has not been done.

### a) Enrollment Visit

Following the provision of informed consent, study subjects will be randomized to one of two arms. A baseline survey will be administered by study nurses, vital signs will be collected and a brief exam will be performed. The medical chart will be reviewed for additional information. A 30 day supply of medications will be provided by study nurse. Contact information will be collected for the woman and a back-up person (with permission) and women will be given an appointment to return in 30 days. Bed nets, condoms and safe sex counseling will be provided. Partner HIV testing will be recommended, discussed with all women and facilitated, as necessary. Questions will be asked by study staff and entered into a RedCAP database. All forms will be labeled with the unique study ID, visit number and date.

Testing: CBC, thick smear and DBS. RPR confirmatory testing for those with + ANC syphilis screen. Vaginal swab for GC/CT and store. pH. Slides and store.

Treatment: For malaria peripheral parasitemia:

1st trimester – Quinine.

National Guidelines: Three doses of Parenteral Quinine base at 8.3mg/kg x 3 every 8 hours for 24 hours. Each infusion should run for 4 hours. This is relayed by Oral Quinine (tablets) for 3 days if patient can tolerate) and a maximum dose of 1.5 per day of Quinine base. The treatment is for 7 days. If the woman develops contractions on quinine, administer tocolytics.

2nd or 3rd trimester - Artesunate.

Per National Guidelines: Injectable Artesunate IV or IM: 2.4mg/kg at 0, 12, and 24 hours. This is continuous once every 24 hours until the patient can take the oral with ease. This is relayed with Artemether -Lumefantrine for 3 days if she can swallow.

1st dose of study medications will be given under directly observed therapy (DOT).

### b) Scheduled Follow Up Visit

Subjects will have vitals and brief exam. If they are noted to be febrile (axillary T>37.5), RDT will be collected. Survey about medication adherence for ART, TMPS, AZ/placebo, pill count, tolerance of prophylaxis and ART, interim treatment, ITN usage. Transportation costs, 30 day medication supply and follow up appointment will be

provided. Contact information will be verified. Questions will be asked by study staff and entered into a RedCAP database.

Testing: DBS for all. RDT if febrile.

Treatment (dosing in section a)):

Malaria with positive RDT: Quinine during the 1st trimester, Artesunate IV during 2nd or 3rd trimester. STI rx from enrollment visit if needed. Syndromic management of STI per routine. DOT ppx meds. Condoms and safe sex counseling will be provided.

**c) Unscheduled Sick Call Visit**

Per routine 24/7 in maternity unit. Vitals and brief exam. Management will be per routine with RDT for fever. Transportation costs will be covered.

If scheduled appointment had been missed – if possible, administer survey about medication adherence and tolerance and outside medications. Provide medications for 30 days. Questions will be asked by study staff and entered into a RedCAP database.

Testing: RDT for fever per routine, DBS for malaria testing (PCR)

Treatment (dosing in section a)):

Malaria with positive RDT: Quinine during the 1st trimester, Artesunate IV during 2nd or 3rd trimester. STI syndromic management. Other antibiotics per routine if recommended by provider and this will be captured as an outcome. DOT of prophylaxis medications if provided.

**d) 35-42 Week Visit**

Vitals and brief exam.

Testing: CBC, RDT, DBS and store, vaginal swab for GC/CT and store, anogenital swab for GBS, vaginal pH, slides and store, rapid syphilis test with RPR confirmation.

Questions will be asked by study staff and entered into a RedCAP database.

Treatment:

Malaria with positive RDT: Artesunate IV (dosing above). GC/CT/Syphilis (same day if possible). DOT of prophylaxis medications. Condoms and safe sex counseling will be provided.

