#### a) Primary Outcomes

**Aim 1** Proportion of women with *Plasmodium falciparum* peripheral parasitemia by microscopy or PCR.

**Aim 2** Prevalence of a composite STI measure (GC, CT, syphilis infections) will be measured in both groups in late pregnancy (>35 weeks gestation) or at delivery and compared between the two groups.

[figure not shown]
**Aim 3** a) Mean infant birthweight; b) Proportion with adverse birth outcomes, including low infant birthweight (<2500 gm), miscarriage (<28 weeks), preterm delivery (<37 weeks), small for gestational age (SGA), stillbirth (>28 weeks), congenital anomaly at birth, early neonatal mortality (within 7 days); and c) maternal adherence to and tolerance of the prophylactic regimen (vomiting, rash/allergic reactions, dizziness, weakness).

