## **XI. SAMPLE SIZE CONSIDERATIONS**

AIM 1: To test the hypothesis that the addition of AZ to standard preventive therapy in pregnant women with HIV will be associated with a lower proportion of women with peripheral parasitemia detected by microscopy or PCR at delivery, we assumed a 30% prevalence of parasitemia in the TMPS arm based on prior studies and 15% prevalence in the TMPS/AZ arm. A sample size of 134 pregnant women per arm has 80% power at a two-sided significance level of 0.05 using a chi-square.

We will plan for 15% loss to follow up (LFU) and will recruit 154 women per arm (308 women total).

AIM 2: Based on the sample size of 308 evaluable participants at the time of delivery and an expected prevalence of 30% for one or more STIs (CT 20%, GC 5%, syphilis 5%) there will be >80% power at a two-sided significance level of 0.05 to detect a 50% lower STI prevalence in the intervention arm.

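### The Aim 2 comparison makes no use of the enrollment syphilis result, and its power statement assumes that the syphilis part of the composite halves along with GC and CT

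*Combined protocol and SAP*

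**What the plan says.** Section III.a sets the Aim 2 primary outcome: "Prevalence of a composite STI measure (GC, CT, syphilis infections) will be measured in both groups in late pregnancy" or at delivery. It gives no case definition for the syphilis component.

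Section VII.d (35-42 Week Visit) lists the late test as "rapid syphilis test with RPR confirmation". The Labor and Delivery and Postpartum visits use the same test if it was not done before. GC and CT are measured by nucleic acid amplification (schedule in Section VII; Section X).

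Syphilis status is also sought at the start. Section VII.a lists "RPR confirmatory testing for those with + ANC syphilis screen", and footnote 4 to the schedule and Section X agree. Section VII.b adds "STI rx from enrollment visit if needed", with no distinction by arm.

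Section XI bases Aim 2 power on CT 20%, GC 5% and syphilis 5%, 30% in all. It opens with "Based on the sample size of 308 evaluable participants at the time of delivery" and concludes that "there will be >80% power at a two-sided significance level of 0.05" "to detect a 50% lower STI prevalence in the intervention arm".

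Section XII plans chi-square or Fisher's exact tests for categorical outcomes. Multivariable modelling is mentioned only for parasitemia and only if the arms are imbalanced. Syphilis at enrollment is not among the potential covariates.

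**The concern.** A woman who is seropositive at enrollment and again late in pregnancy may be counted as an event in either arm, for reasons that predate randomisation. If such women are equally common in both arms and azithromycin does not change their late result, they add the same amount to both rates. The difference between arms is then smaller than the power statement assumes.

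The unadjusted test treats this predictable part of the outcome as noise, although the trial holds the variable that identifies it. At stake is power for one of the three primary aims, and how a smaller-than-planned difference would be read. Type I error is not affected.

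**Working it through.** **Inputs.** Control rate 30% = 20% + 5% + 5%, a simple sum without overlap (Section XI). Two-sided alpha 0.05. Evaluable women per arm: 154 (Section XI, 308 in all) or 134 (Section XIII, 268 in all after losses). Assumption: a share f of the 5% late syphilis positivity was already present at enrollment, is equal in both arms and is unchanged by azithromycin. The documents give no value for f, so the range is 0-100%.

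**Formula (uncorrected chi-square).** Power = Φ[(d − 1.96·SE0)/SE1], where d = p1 − p2, SE0 = √(2p̄(1−p̄)/n) and SE1 = √((p1(1−p1) + p2(1−p2))/n).

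**Plan's own figure.** For 30% v 15% at n = 154: SE0 = 0.04759, SE1 = 0.04681, (0.15 − 0.09327)/0.04681 = 1.212, power 88.7%. This agrees with the stated figure of over 80%. At n = 134: (0.15 − 0.09999)/0.05019 = 0.997, power 84.0%.

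**Intervention rate with carry-over.** CT and GC halve, 25% → 12.5%. Syphilis becomes 2.5%·(1−f) + 5%·f. So p2 = 15% + 2.5%·f.

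| f | p1 v p2 | Power, 154/arm | Power, 134/arm |
|---|---|---|---|
| 0 | 30% v 15% | 88.7% | 84.0% |
| 25% | 30% v 15.6% | 85.6% | 80.4% |
| 50% | 30% v 16.25% | 82.0% | 76.4% |
| 100% | 30% v 17.5% | 73.4% | 67.3% |

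At f = 100% the relative reduction is 12.5/30 = 41.7%, not 50%. Power passes below 80% at f of about 62% with 154 per arm and about 28% with 134 per arm.

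**Continuity correction.** The Aim 1 figure of 134 per arm is reproduced only with the correction (121 without it), so corrected values are relevant too. From f = 0 to f = 100%, corrected power goes from 85.8% to 68.8% at 154 per arm and from 80.2% to 61.9% at 134 per arm. The 80% thresholds are about 39% and about 1%.

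**What stratifying recovers.** Suppose every carry-over woman is positive at both times. Her stratum then holds only events and adds nothing to a Cochran-Mantel-Haenszel test, so the comparison rests on the other women. Starting from 134 per arm:
- f = 100%: n = 134 × 0.95 = 127.3; rates 25/95 = 26.3% v 12.5/95 = 13.2%; (0.1316 − 0.0978)/0.0492 = 0.687, power 75.4%, against 67.3% unadjusted.
- f = 50%: n = 134 × 0.975 = 130.65; rates 27.5/97.5 = 28.2% v 13.75/97.5 = 14.1%; (0.1410 − 0.0990)/0.0498 = 0.844, power 80.1%, against 76.4%.

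Simulation of the two tests agrees: 77% → 81% at f = 50%, 68% → 76% at f = 100%, and no loss at f = 0.

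**GC and CT alone.** 25% v 12.5% gives 80.5% at 154 per arm and 74.9% at 134 per arm. This suits a sensitivity analysis, but it does not rescue power as a replacement outcome.

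**The case against.** The strongest reply is that prevalence is what the plan sets out to measure. The Protocol Summary and Section III.a both say so. The Background describes intermittent prophylaxis as also treating silent infections, and reports azithromycin activity against syphilis in certain populations. Infection present at enrollment is therefore within scope. GC and CT present at enrollment stay in the composite as well, so restricting syphilis alone to new infection would make the components inconsistent. This stands, and it is why the outcome itself should be left as it is.

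It is also fair that syphilis is only 5 of the 30 points, that the trial is a Phase II test of concept, and that at the plan's own 308 evaluable women more than about 62% of late positives must be carry-over before uncorrected power drops below 80%.

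A reader might infer more than the documents support:
- *That any late positive serology counts by rule.* The plan requires RPR confirmation and is otherwise silent on what makes a case. The Labor and Delivery section separates untreated earlier infections from newly detected ones, but only for treatment.
- *That infections found at enrollment are known to be treated and still counted.* The enrollment section lists treatment for malaria only. STI treatment is implied by the follow-up section. No passage says how often RPR stays positive after treatment.
- *That Aim 2 is underpowered.* That depends on f, which is not given. Moving from 154 to 134 per arm lowers power from 88.7% to 84.0% with no carry-over at all. That is a separate inconsistency and is not due to syphilis.

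None of this explains why a baseline result already in hand is left out of the comparison, or why the power statement does not mention that it halves the syphilis part.

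**Conclusion.** The point holds as an avoidable loss of efficiency and an unstated power assumption. Depending on f, power at 154 per arm lies between 88.7% and 73.4%, and at 134 per arm between 84.0% and 67.3% (uncorrected). At 134 per arm, stratifying by enrollment status regains about 4 points if half the late syphilis is carry-over and about 8 points if all of it is. It costs nothing if none is. It does not restore 80% in the extreme case.

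These figures rest on additive components, GC and CT halving as planned, equal carry-over in both arms with no effect of azithromycin on it, and, for the gain, enrollment-positive women remaining positive late. If some become negative, both the dilution and the gain are smaller. The documents do not establish that power is below 80%.

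**What to change.** 1. Keep late prevalence of GC, CT or syphilis as the Aim 2 primary outcome. In Section XII, specify that the arms are compared with stratification by, or adjustment for, enrollment syphilis status, for example by a Cochran-Mantel-Haenszel test. Give the crude proportions and their difference beside it. The enrollment-positive stratum may be small (0.05 × 134 = 6.7 women per arm if all of the 5% is carry-over) and nearly all events. The stratified test copes with that better than a logistic model, which may not converge.
2. Define enrollment-positive from the antenatal screen and RPR already planned, and say how women without an enrollment result are classified.
3. Add a GC/CT-only composite as a sensitivity analysis.
4. Report late syphilis positives by arm, split by enrollment status.
5. In Section XI, state that the power of over 80% assumes the syphilis component also halves, and show the range above.

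Do not make new infection or a titre rise the primary syphilis definition. The plan states prevalence, GC and CT would remain prevalent measures, and no passage promises RPR titres.

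The cost is a few sentences, settled before unblinding, and carrying the enrollment result into the analysis dataset. No sample, visit or test is added.

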**e) Labor and Delivery Visit**

Vitals and brief exam.

Testing (if not performed at 35-42 weeks): CBC, thick smear, DBS and store, vaginal swab for GC/CT and store, anogenital swab for GBS, vaginal pH, slides and store, rapid syphilis test with RPR confirmation. Collect placentas, OK to refrigerate overnight.

Biopsy specimen placed in formalin and can be stored on site. Questions will be asked by study staff and entered into a RedCAP database.

Treatment:

Malaria with positive RDT or peripheral parasitemia: Artesunate IV. GC/CT/syphilis if not yet treated from prior visit or newly detected. Ampicillin IV for GBS positive (late pregnancy screen or L+D screen). Treat maternal/neonatal infection per routine.

Survey: FU survey with questions about medication adherence, tolerance, interim medications and source.

Study RN: outcome assessment form including infant weight with electric scale, GA, maternal/neonatal infection, surface examination for major congenital anomalies. Verify contact information – plan to call after 7 days to ask about neonatal mortality. Recommend infant HIV testing.

**f) Postpartum visit – 0-14 days with baby**

For women who did not deliver at the facility.

Testing: if not done prior (35-42 wk or at delivery) - CBC, thick smear, DBS and store, vaginal swab for GC/CT and store, anogenital swab for GBS, vaginal pH, slides and store, rapid syphilis test with RPR confirmation. No testing if it was done previously. Questions will be asked by study staff and entered onto paper forms for later entry into a RedCAP database.

Treatment: infection detected on current testing or prior testing if not yet treated.

Survey: Follow-up survey about medication adherence, tolerance, interim meds and source.

Study RN: outcome assessment form – review patient medical record (document source of info) and capture birth weight. Ask about maternal/neonatal infections. Perform surface exam for major congenital anomalies. Verify contact information – may need to come back for treatment if testing performed and any new infections noted.

